Study Title:

The Accuracy of Smartphone Pulse Oximetry in Patients Visiting an Outpatient Pulmonary Function Lab for a 6-Minute Walk Test

Primary Investigator:

[name], RRT-ACCS, AE-C, FAARC, FCCP
Director of Clinical Education
Assistant Professor
Rush University, Department of Respiratory Care

Co-Investigator:

[name]
M.S. in Respiratory Care | Class of 2018
Department of Respiratory Care
Rush University Medical Center

[name], MS, RRT, RPFT
Pulmonary Function Lab
Rush University Medical Center

October 13, 2019

Aim of the Study

The primary aim of this research is to determine the accuracy of smartphone pulse oximeters in detecting blood oxygen saturations, episodes of desaturations, and heart rate by comparing results to a Masimo[©] hospital-grade pulse oximeter.

Introduction

Digital innovations have made it possible for consumers to use mobile devices for medical purposes. They can be used to monitor physiological parameters such as blood pressure, heart rate, blood oxygen saturation, and body temperature. They can also be used to conduct diagnostic tests, request prescription refills, and relay medical information to physicians.¹ Consequently, the healthcare sector is being profoundly affected by this emerging technology.^{1,2} A frequent reliance on mobile devices has been reported among healthcare practitioners (HCPs) and students, with 85% reporting the use of a mobile device at least once daily for clinical purposes. The most common use was for information, time management, or communication relating to education and patient care.³ In 2010, approximately 50 percent of physicians used a mobile phone or a smart mobile device as a part of his or her practice. In 2015, that number increased to approximately 70 percent. The overall growth of applications (apps) was 38.1 percent, compounded annually over the past five years; in regards to medical apps, the growth was documented at 41.9 percent.⁴

Various cell phone companies have created and embedded pulse oximetry apps in smart phones that enable individuals to monitor their oxygen saturation and vital signs. Samsung, Apple, and various other companies have designed cellular devices that are capable of providing health-related apps. Other developers have created apps that are compatible with Android and iOS technologies. Some companies, including Lionsgate Technologies and Masimo, have developed external pulse oximeters that are compatible with smartphones. While these features seem promising for use of home monitoring of blood oxygen saturation levels, the accuracy of many of these features and devices have not yet been established.

Smartphone pulse oximeters and other mobile health (mHealth) apps are examples of new and evolving technology, which if developed accurately and used correctly, may make a difference in the lives of many individuals. A study conducted by Petersen et al suggests that if pulse oximeters could be available on mobile phones many global infectious diseases, such as pneumonia in children, could be treated faster and mortality rate would thus decrease due to prompt detection of changes in vital signs alongside quicker treatments.^{5,6} Studies from both Canada and Uganda regarding the Phone Oximeter prototype (a device interfacing pulse oximeters and smartphones) provide an overall usability scores of 82 percent and 78 percent respectively, indicative that a phone could be a functional oximeter interface.⁷ A usability score of > 75% is considered appropriate as a functional interface. Additionally, a blinded randomized control trial in Australia, revealed that self-monitoring of oxygen saturation via a telehealth app Breathe-easy[©] reduced exacerbations of asthma in pregnant women.⁸ Since the severity of asthma increases during pregnancy commonly, Zairaina et al studied monitoring in pregnant women and found that it improved quality of life, although it did not impact lung function.⁸

Alexander et al compared four different smartphone application-based monitors: Instant Blood Pressure, Instant Blood Pressure Pro, Pulse Oximeter, and Pulse Oximeter Pro. Three different parameters were measured using these four devices: heart rate, blood pressure, and SpO₂. The comparison revealed a large degree of variance in the values between the Instant Blood Pressure, the Instant Blood Pressure Pro, the Pulse Oximeter, and the Pulse Oximeter Pro.⁹ Another study by Petersen and Dumont was conducted that compared the response of motion artifact of three different mobile pulse oximeter devices, all interfaced to Apple iPod Touch devices: the Nonin Xpod, the Masimo OEM inline module, and an Audio Phone Oximeter prototype. The study showed that there was more motion artifact at lower saturations for all three of the devices. The most valid measurements was found with Masimo's mobile device at readable values of approximately 85 to 87 percent.¹⁰

While the technology to detect SpO₂ and heartrates on smartphones is emerging and widely available, there is no evidence supporting its use in patients with lung disease. Smartphone pulse oximetry could be useful in individuals with acute or chronic lung disease; however, device inaccuracies could be harmful if desaturations are not detected immediately. It is not known how accurately these devices detect oxygen saturation/desaturation in patients with acute or chronic lung conditions. This study will be used to evaluate the accuracy of smartphone pulse oximeters in patients that will be undergoing a six-minute walk test in a pulmonary function lab.

Experimental Design and Methods

This is a prospective, observational study conducted at the pulmonary function laboratory at Rush University Medical Center. Subjects (n=48) will be selected if they are of 18 years of age or older, ambulatory, scheduled for a six-minute walk test, and agree to participate. The following information will be collected:

- First name
- Last name
- Date of Birth
- Age
- Height
- Gender
- Race/Ethnicity
- Oxygen use and frequency (if they are already on oxygen)
- Pulmonary Disorders
- Borg's Dyspnea Scale
- Heart rate (hospital-grade pulse oximeter and external and built-in smartphone pulse oximeter; pre- and post- test)
- SpO₂ (hospital-grade pulse oximeter and external and built-in smartphone pulse oximeter; pre- and post- test)

Procedures

For every patient that meets inclusion criteria, demographic information such as: age, race, and gender will be collected. Weight will be measured in the pulmonary function clinic by the designated respiratory therapist. Heart rate and SpO₂ measurements will be taken per normal routine during the six-minute walk test (before and after the test). Parameters will be measured

using an iPhone attached external pulse oximeter (Kenek Edge, LionsGate Technologies, Vancouver, Canada), a Samsung S8 (Samsung Electronics Co. Inc., Seoul, South Korea) built-in pulse oximeter, and a Masimo[®] (Masimo Corporation, Irvine, California) hospital-grade pulse oximeter. Readings will be obtained before and after the test. All three devices will be used to obtain readings from a single arm, consecutively. Each reading will be recorded manually by persons involved in the research. Each reading will be recorded using RedCap software and later transferred to SPSS software for data analysis. All data placed on the RedCap software and SPSS will only be accessible by the primary investigators.

Subject Population

Inclusion criteria

Ambulatory patients, 18 years and older, visiting the pulmonary function laboratory at Rush University Medical Center for a 6-minute walk test (n = 30) that agree to participate.

Exclusion criteria

Patients who are under the age of 18 years or patients with high blood pressure above 180/90 mm Hg or pressure below 70/50 mm Hg will be excluded. Patients who are dizzy, light-headed or have severe headaches, if SpO₂ at or below 85% on supplemental oxygen or if patients are on oxygen greater than 4 liters per minute will be excluded. Gait issues that may result in a fall or patient walks with a walker and did not bring the device to this visit will be excluded.

Consent and Recruitment Procedure

Recruitment will be based on inclusion and exclusion criterion. Study subjects will be recruited through convenience sampling of patients attending the pulmonary function lab for a 6-minute walk test at Rush University Medical Center. Verbal consent will be obtained during the time of subject interaction. Waiver of written consent will be requested since no invasive procedures are involved or procedures that would potentially be harmful to the participants.

Compensation

There is no compensation provided in this study. The participant is not required any other follow up after obtaining this initial data.

Special Precautions

There are no special precautions needed in this study. Standard disinfection policies apply. Personal protective equipment and standard protocol should be followed at all times. Patient safety and privacy will be addressed at all times.

Confidentiality

Persons who are primary investigators and secondary investigators, along with the IRB, will have access to patient records. To protect patient privacy and confidentiality, each patient will be assigned a subject identification number. Names will not be included in the data analysis. The investigators will strictly adhere to HIPAA and IRB guidelines to ensure that patient confidentiality is maintained.

Plans for Data Analysis

Data for each subject will be recorded in RedCap which will only be accessed by study investigators. Means and standard deviation will be calculated for age, gender, race, heart rate,

and pulse oximeter reading from hospital-grade and smartphone pulse oximeters. A t-test will be used to determine any significant association between age, gender, diagnosis, weight, and oxygen use ($p < .05$). Alpha will be used as 0.05 and beta will be used as 0.20. It can be predicted that these tests will be parametric. A scatter plot will be used to assess bias and validity.

Independent variables: Type of pulse oximeter

Dependent variables: SpO₂ and heart rate

Co-variables: body mass index, admitting diagnosis, age, site of measurement, oxygenation status, skin pigmentation, nail color, and pulmonary disorders.

References

1. Topol E. How technology is transforming healthcare. 2013;2017(08/02). Web.
2. Huston C. The impact of emerging technology on nursing care: warp speed ahead. *Online J Issues Nurs* 2013;18(2):1.
3. Ventola CL. Mobile Devices and Apps for Health Care Professionals: Uses and Benefits. *P T* 2014;39(5):356-364.
4. Heath S. mHealth App Market Sees \$400 Million Growth in Five Years. 2015;2017(08/03). Web.

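### The primary aim includes detecting desaturation, but the analysis plan has no desaturation outcome, cut-off or detection rate, and episodes that end before the post-walk reading are not captured

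*Combined protocol and SAP*

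**What the plan says.** **Aim.** Aim of the Study sets out to "determine the accuracy of smartphone pulse oximeters in detecting blood oxygen saturations, episodes of desaturations, and heart rate", with a Masimo hospital-grade oximeter as the comparator. Desaturation episodes are listed separately from saturation level and heart rate. The Introduction gives the gap in knowledge: "It is not known how accurately these devices detect oxygen saturation/desaturation in patients with acute or chronic lung conditions".

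**Data.** Experimental Design and Methods lists SpO₂ from all three devices, before and after the test. Procedures states: "Readings will be obtained before and after the test". An earlier sentence there places the measurements in the course of the walk test, but its own parenthesis limits them to before and after. The Appendix form has one pre-test and one post-test SpO₂ cell per device. It has no field for a reading during the walk, a lowest value or an episode, even for the Masimo. On how the readings are taken, Procedures says: "All three devices will be used to obtain readings from a single arm, consecutively".

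**Analysis.** Plans for Data Analysis names oximeter type as the independent variable and SpO₂ and heart rate as the dependent variables. The methods it states are means and SDs, a t-test relating patient characteristics, and a scatter plot for bias and validity.

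**Cut-offs.** The only SpO₂ cut-off in the plan is in the Exclusion criteria, "if SpO₂ at or below 85% on supplemental oxygen". It governs eligibility and does not define desaturation.

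**The concern.** How closely a phone reads SpO₂ on average and how often it misses a low value are different questions, and the aim asks both. Only the first has anything resembling a planned analysis. At the end of the study there would be no figure for missed low values, and a reader could take a small average difference as evidence that the phones detect desaturation.

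There are two gaps, and they differ in kind. The missing detection analysis can be repaired, because the paired post-walk readings are already to be collected. The missing readings between the two time points cannot be repaired by analysis. For those, the aim has to match what is recorded.

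**Working it through.** **1. Aim against data and analysis.**

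| Part of the aim | Recorded for the study | Planned result |
|---|---|---|
| SpO₂ level | Pre and post, three devices | Means, SDs, scatter plot |
| Heart rate | Pre and post, three devices | Means, SDs, scatter plot |
| Desaturation present at the post-walk reading | Yes, as an SpO₂ value | None: no definition, cut-off or rate |
| Desaturation resolved before the post-walk reading | No | None possible |

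The plan gives no figure on this point, so there is nothing to reproduce.

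**2. Can the average stand in for a miss rate?** Illustration, with assumed values: a phone is exact in patients who are not low and reads 5 points too high in a fraction p who are low.

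- Mean difference = 5p: 0.5 points at p = 0.10 and 2.5 points at p = 0.50.
- SD of the differences = 5 × √(p(1−p)) × √(n/(n−1)), so a paired t = √(p/(1−p)) × √(n−1).
- p = 0.10: 0.333 × √29 = 1.8 (n=30) and 0.333 × √47 = 2.3 (n=48).
- p = 0.50: √29 = 5.4 (n=30) and √47 = 6.9 (n=48).

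When few patients are low, the shift is half a point and t lies close to the 5% critical value of about 2, so masking is plausible. When half are low, the shift is plain. In neither case does the mean give a miss rate. The scatter plot would show the discrepant points, but without a cut-off it does not count them.

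**3. What a detection rate could deliver.** The documents give two sample sizes (48 in Experimental Design and Methods, 30 in Inclusion criteria) and no expected rate of low saturation. Assumptions: 10% to 50% of patients are low on the post-walk Masimo reading, and the phone detects about 80% of them (nearest whole count). The exact (Clopper-Pearson) limits for x detected of m low are the 0.025 quantile of Beta(x, m−x+1) and the 0.975 quantile of Beta(x+1, m−x).

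| n | Low, assumed | Events m | Detected x | Exact 95% CI |
|---|---|---|---|---|
| 48 | 10% | 4.8, rounded to 5 | 4 | 28% to 99% |
| 48 | 20% | 9.6, rounded to 10 | 8 | 44% to 97% |
| 48 | 30% | 14.4, rounded to 14 | 11 | 49% to 95% |
| 48 | 50% | 24 | 19 | 58% to 93% |
| 30 | 10% | 3 | 2 | 9% to 99% |
| 30 | 20% | 6 | 5 | 36% to 100% (99.6% before rounding) |
| 30 | 30% | 9 | 7 | 40% to 97% |
| 30 | 50% | 15 | 12 | 52% to 96% |

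These intervals measure the precision of the added analysis. They do not measure the size of the gap in the present plan.

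**The case against.** **Episodes is undefined.** The aim does not promise continuous monitoring or a lowest value. A fall from the pre-walk to the post-walk reading is a fair meaning of the word, and the form collects exactly that. This stands, and it is why the missing detection analysis is the main point. It does not close the gap, because on that meaning too the plan has no outcome and no rate.

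**The plan already compares devices.** It names oximeter type as the independent variable, and its scatter plot may show error at low values. That is fair: the comparison of SpO₂ and heart rate is intended. The plot still yields no count of missed cases.

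**Too few events.** With 3 to 5 low patients, sensitivity is close to uninformative. This also stands, and it is a reason to report the interval with the estimate. Leaving the result out would hide the uncertainty.

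**Stronger readings that a reader might infer, and that the documents do not support.**

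- *That SpO₂ is not watched during the walk.* The documents do not say what the lab does in routine care. They show only that nothing from that period is recorded for the study.
- *That the study fails to measure speed of detection.* The remark that "device inaccuracies could be harmful if desaturations are not detected immediately" is background in the Introduction. The aim claims accuracy, not speed.
- *That averages would conceal the problem generally.* By the arithmetic above, a 2.5-point shift would be visible.

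**Conclusion.** The point holds. Desaturation detection is part of the primary aim, and the plan as written produces no result for it. In addition, an episode that resolves before the post-walk reading lies outside the recorded data.

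A reader might go further and conclude that the study can say nothing about desaturation. The documents do not support that: low saturation still present after the walk is captured by all three devices and can be analysed.

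The absence of an outcome, a cut-off and a rate is read directly from the text and rests on no assumption. The interval widths rest on the assumed 10% to 50% low and the observed sensitivity near 80%. The masking illustration rests on the assumed 5-point error. This is a change the investigators should make. It does not invalidate the planned SpO₂ and heart-rate comparisons.

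**What to change.** (a) **Reword the aim** to low saturation, or a pre-to-post fall, present at the post-walk reading. State that episodes resolving earlier are not studied.

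(b) **Add one analysis.** The investigators fix one analysis cut-off before data are seen, the same for Masimo and both phones. If data have already been seen, label the analysis post hoc. The choice of value is theirs, and it serves only to classify readings. For each phone, report the post-walk 2x2 table against Masimo with sensitivity, specificity and exact 95% CIs. Show patients already low at the pre-walk Masimo reading separately. Some are plausible because oxygen users are enrolled, and they are not newly desaturated. If a pre-to-post fall is also reported, note that a change score cancels a constant device offset.

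(c) **State a limitation.** The devices are read one after another and no order is given. Recovery between readings can look like a miss if the Masimo is read first, or like a false alarm if the phone is read first. Device order and timing affect every comparison in the study and are a separate matter.

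**Cost.** A change of wording and one analysis of values already planned for collection, with no new measurement. The downside is a narrower aim and wide intervals, which widen further once resting-low patients are split off. The two sample sizes also need reconciling, since the expected number of events depends on which applies.

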Appendix

Subject ID _____

Gender Male Female Transgendered

Ethnicity White/Caucasian
 Hispanic/Latino
 Black/African American
 Asian
 Other (specify) _____

Age _____

Weight (lbs) _____

Diagnosis Asthma
 Congestive obstructive pulmonary disorder (COPD)
 Cystic Fibrosis
 Pulmonary Fibrosis
 Chronic Bronchitis
 Bronchiectasis
 Congestive Heart Failure
 Stroke
 Heart Attack/Failure
 Pulmonary Hypertension
 Cancer
 Renal Disease
 Other (specify) _____

Oxygen use? Yes No

If yes, indicate the amount of oxygen used

○ ○ ○ ○ ○
< 2L/min flow 2-6 L/min flow 6-10 L/min flow As needed Only after physical activity

	Pre-test Vital Signs			Post-test Vital Signs		
	Masimo	Kenek/Apple	Samsung	Masimo	Kenek/Apple	Samsung
Heart Rate						
SpO ₂						
Blood Pressure						
RR						
Borg Dyspnea Scale

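### With a single Masimo pulse-oximeter reading per time point as the only reference, the design can show agreement with the Masimo but not accuracy for blood oxygen saturation

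*Combined protocol and SAP*

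**What the plan says.** The Aim of the Study reads: "determine the accuracy of smartphone pulse oximeters in detecting blood oxygen saturations, episodes of desaturations, and heart rate by comparing results to a Masimo", the comparator being a hospital-grade unit. The title also speaks of accuracy, and the last paragraph of the Introduction says the study will evaluate accuracy in patients having a six-minute walk test.

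Procedures names three devices: a phone-attached external oximeter, a phone with a built-in oximeter, and the Masimo "hospital-grade pulse oximeter. Readings will be obtained before and after the test". On timing it says: "All three devices will be used to obtain readings from a single arm, consecutively". It gives neither the order of the devices nor the interval between readings.

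The Appendix form has a "Pre-test Vital Signs" block and a matching post-test block. Each has one SpO₂ cell and one heart-rate cell per device. No arterial saturation or ECG measure appears in the data list, the procedures or the form.

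For the comparison itself, Plans for Data Analysis says: "A scatter plot will be used to assess bias and validity". It makes no allowance for error in the reference, and no section states a limitation of using the Masimo as the reference.

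**The concern.** A claim of accuracy for blood saturation needs a reference whose error is negligible or known. Here the reference works on the same principle as the devices under test, and it is read once per time point. Two problems follow, and they act in opposite directions.

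- **Shared error is hidden.** If a patient feature shifts the phone and the Masimo alike, their difference does not move and the phone looks accurate.
- **Unshared error is charged to the phone.** Random Masimo error, and any true change in saturation while one device is swapped for the next, widen the phone-Masimo scatter. The report would present this as phone inaccuracy.

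The second problem is likely to matter most after the walk, when saturation may be recovering between readings. Those are also the readings on which the desaturation part of the aim depends. The pre-walk and post-walk Masimo readings cannot serve as replicates, because they are taken in different physiological states. The same reasoning applies to heart rate.

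At stake is the wording of the conclusion and the means to interpret it. Without a Masimo-against-Masimo figure, a reader cannot tell whether phone-Masimo scatter exceeds what the Masimo shows against itself.

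**Working it through.** **The plan's own figures.** The plan gives no figure for device error, agreement or an acceptable difference, so there is nothing to reproduce. It gives alpha 0.05, beta 0.20 and two sample sizes (48 and 30) with no effect size. The point does not depend on the sample size.

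**Model for one time point.** Let T be the true saturation when a device is read, b the device's own bias, c the error common to both devices, and e the random reading error:

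- Masimo: M = T_M + b_M + c + e_M
- Phone: P = T_P + b_P + c + e_P
- Difference: P − M = (b_P − b_M) + (T_P − T_M) + (e_P − e_M)

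**Step 1: shared error.** The term c drops out. If both devices over-read by a hypothetical 3 points, the observed bias is 3 − 3 = 0. No sample size changes this.

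**Step 2: Masimo noise.** With independent errors and no true change between readings, Var(P − M) = s_M² + s_P². The 95% limits around the mean difference are ±1.96·√(s_M² + s_P²), against ±1.96·s_P for the phone alone. The documents give no SDs, so the following values are assumptions in SpO₂ points:

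| s_M | s_P | Variance of difference | Masimo share | 95% limits | Phone alone | Ratio |
|---|---|---|---|---|---|---|
| 0.5 | 2 | 0.25 + 4 = 4.25 | 0.25/4.25 = 6% | ±4.0 | ±3.9 | 1.03 |
| 1 | 1 | 1 + 1 = 2 | 1/2 = 50% | ±2.8 | ±2.0 | 1.41 |
| 2 | 2 | 4 + 4 = 8 | 4/8 = 50% | ±5.5 | ±3.9 | 1.41 |
| 1.5 | 1 | 2.25 + 1 = 3.25 | 2.25/3.25 = 69% | ±3.5 | ±2.0 | 1.80 |

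The share runs from negligible to dominant, and the documents do not say where in that range the study lies.

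**Step 3: true change between readings.** T_P − T_M is zero only if saturation is steady while the devices are swapped. If it is not, its mean enters the apparent bias and its variance adds to the sum in step 2.

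**Step 4: desaturation.** The documents define no threshold. Assume true SpO₂ has mean 93 and SD 4, the cut-off is 88, and a phone has no error at all. Its apparent sensitivity against the Masimo is P(T ≤ 88 and M ≤ 88) / P(M ≤ 88), with M = T + e_M, bivariate normal. For s_M = 1, 2 and 3 this is 0.81, 0.62 and 0.47. The whole shortfall from 1 is reference error.

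**Step 5: what a second Masimo reading adds.** With s_M = s_P = 1, comparing the phone with the mean of two Masimo readings gives variance 1 + 1/2 = 1.5 and limits of ±1.96·√1.5 = ±2.4, instead of ±2.8. The two Masimo readings differ from each other with variance 1 + 1 = 2, so the Masimo-Masimo limits are ±2.8 if saturation is steady. That pair is a direct check on s_M, which the current form does not provide.

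**The case against.** **The comparator is disclosed.** The sentence that claims accuracy also names the Masimo, and the outcome is labelled SpO₂. The documents nowhere say that the Masimo is taken as true saturation. This stands, so the first part of the fix is mainly wording. But naming the comparator does not turn agreement into accuracy, and the title makes the claim without the qualifier.

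**The documents favor the Masimo.** A reader might take the Introduction's remark on an earlier comparison, "The study showed that there was more motion artifact at lower saturations for all three of the devices", as evidence against this reference. It is weak evidence. That study tested motion artifact in a Masimo module attached to a mobile device, whereas here a hospital-grade unit is read before and after the walk. The next sentence of the Introduction reports that the most valid readings came from the Masimo device. It is a reasonable comparator, but nothing in the documents shows that it is free of error.

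**Skin pigmentation.** The covariate list includes "oxygenation status, skin pigmentation, nail color, and pulmonary disorders", and reference 6 is titled "Effects of skin pigmentation on pulse oximeter accuracy at low saturation". A reader might infer that the study will report a pigmentation effect on accuracy, or that the Masimo over-reads in dark skin. The documents support neither. No analysis using pigmentation is named. Neither pigmentation nor nail color is in the data list or on the form, which records only ethnicity. Only the title of reference 6 is visible, and it gives no direction of error and names no Masimo.

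**Masimo error could be separated anyway.** With three devices and independent errors, a Grubbs-type calculation can estimate it, so it would be too strong to say it cannot be estimated. But no such analysis is planned, and it is imprecise. In simulation with a true Masimo variance of 4 (phone SDs 2 and 3), 95% of estimates fell between 1.1 and 7.6 at n = 48, and between 0.3 and 8.2 at n = 30. It also cannot recover shared error.

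**The sizes are assumed.** This stands: every SD above is an assumption. One reading per time point is likewise inferred from the form, because Procedures does not fix the number.

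**Conclusion.** The point holds as a limit on what may be concluded. As designed, the study can report agreement with a Masimo pulse oximeter. It cannot report accuracy for blood oxygen saturation.

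That shared error cancels, and that reference noise and true change enter the difference, follows from the design and needs no assumed figure. The size does need one. With independent errors of 1 point SD each and steady saturation, the limits are ±2.8 against ±2.0, or 41% wider. Over the assumed ranges (Masimo SD 0.5 to 1.5, phone SD 1 to 2), the Masimo's share of the variance runs from 6% to 69%.

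This is a cheap improvement, not a flaw that defeats the study. The documents do not show that the Masimo is a poor comparator, and they state no acceptability criterion that reference noise would cause a phone to fail.

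**What to change.** 1. **Wording.** State the title, aim and conclusions as agreement with the hospital-grade Masimo. List the lack of a blood reference as a limitation, and say that error common to all three devices cannot be seen.
2. **Bracketing.** At each time point, read the Masimo, then the two phones, then the Masimo again. Add one Masimo column to the pre-test block of the form and one to the post-test block. Compare each phone with the bracketing Masimo readings, for example their mean, and report bias with 95% limits of agreement. Report the Masimo-Masimo difference alongside as the benchmark, separately before and after the walk, noting that it includes true change over the interval. A repeat at rest only would miss the post-walk setting on which the desaturation aim depends.

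The cost is protocol wording, two form columns and one extra noninvasive reading per time point with a device already in use. The downside is a more modest claim. The second Masimo reading shows repeatability and change over the interval. It does not reveal bias shared with the phones, so the limitation in item 1 is still needed.

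### The protocol gives two sample sizes, 48 and 30, for the same study population, and nothing in it reconciles them

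*Combined protocol and SAP*

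**What the plan says.** Two places in the combined protocol and SAP give a number of subjects.

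- Experimental Design and Methods: "Subjects (n=48) will be selected if they are of 18 years of age or older, ambulatory". The sentence goes on to require that they are scheduled for the walk test and agree to take part. The section names the pulmonary function laboratory at Rush University Medical Center as the site.
- Subject Population, Inclusion criteria: "Ambulatory patients, 18 years and older, visiting the pulmonary function laboratory at Rush University Medical Center", and then "for a 6-minute walk test (n = 30) that agree to participate".

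Three other sections bear on how the numbers could be read.

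- Procedures: "Readings will be obtained before and after the test. All three devices will be used to obtain readings from a single arm, consecutively". Every patient contributes readings from every device at both times.
- Consent and Recruitment Procedure: "Study subjects will be recruited through convenience sampling of patients attending the pulmonary function lab for a 6-minute walk test". One sample is described.
- Plans for Data Analysis: "Means and standard deviation will be calculated for age, gender, race, heart rate", followed by the oximeter readings from the hospital-grade and smartphone devices. The only statement resembling a sample-size basis is "Alpha will be used as 0.05 and beta will be used as 0.20". It comes with no n, effect size, SD or sidedness, and the only test named is a t-test for associations among patient characteristics.

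**The concern.** Both sentences define the same people: adults, ambulatory, attending the same laboratory for the same test, and agreeing to participate. One population cannot have two planned sizes unless the protocol says what each number counts, and it does not.

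What is at stake is the definition of a completed study. Recruitment is by convenience, and the plan gives no other point at which it ends. With two targets in the text, neither the investigators nor a later reader can say whether stopping at 30 was planned or was a shortfall, and the choice could be made after data have been seen.

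**Working it through.** **Inputs from the document.** n = 48 (Experimental Design and Methods); n = 30 (Inclusion criteria); 3 devices and 2 time points (Procedures); alpha 0.05 and beta 0.20 (Plans for Data Analysis). The document gives no effect size, SD, sidedness, agreement limit or dropout rate, so neither sample size can be reproduced.

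**Size of the gap.**
- 48 − 30 = 18 patients.
- 18/48 = 37.5%: 30 is 37.5% below 48.
- 18/30 = 60%: 48 is 60% above 30.

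**Could the two numbers both be right?**

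| Possible reading | What the text shows |
|---|---|
| 48 approached, 30 consenting | Both sentences already require agreement, and the section giving 48 lists the device readings to be collected on those subjects. |
| Groups by device | All three devices are read on each patient. |
| Separate cohorts, or 30 as a subgroup | One convenience sample is described and the defining criteria match. |
| 48 is 30 inflated for losses | 30/(1 − d) = 48 gives d = 1 − 30/48 = 37.5%. No loss rate is stated. Assumed rates of 10%, 20% and 30% give 34, 38 and 43. The Compensation section says no follow-up is required after the initial data. Losses within the visit, such as an unfinished walk or a failed reading, are possible, but no allowance is made for them. |
| One number superseded | There is no amendment log or note to that effect. |

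**Does beta 0.20 identify n?** To test this I assumed a paired t-test, which the plan does not specify. At 80% power the detectable mean difference, in SDs of the paired differences, is:

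| Alpha 0.05 | n = 48 | n = 30 |
|---|---|---|
| Two-sided | 0.413 | 0.529 |
| One-sided | 0.364 | 0.465 |

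Each n has 80% power for some effect. With no target effect stated, beta is compatible with either number.

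**What follows from the gap.**
- Readings per outcome (SpO₂, and likewise heart rate): 48 × 3 × 2 = 288; 30 × 3 × 2 = 180; difference 108.
- Standard error of a planned device mean at equal SD: √(48/30) = √1.6 = 1.265, so 26% larger at 30.

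These last figures restate the ratio 48/30 in practical terms. They are not separate evidence of a fault.

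**The case against.** The best reconciling reading is exclusion on the day. The sentence with 48 refers to patients scheduled for the test, while the sentence with 30 refers to patients visiting for it. Several exclusions (blood pressure, symptoms, oxygen saturation or flow, gait) may become apparent only at the visit. On that reading 48 are selected and 30 remain. The text does not support it: the 30 sits in the inclusion sentence, ahead of the exclusions, and is not described as a remainder. Consent is taken during the interaction with the patient, so agreement comes at the same point under both sentences. Even if this reading were intended, the numbers would still need labels.

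A second objection is about weight. This is a single-visit observational study with no randomisation, interim look or stopping rule. Either number leaves the planned analyses unchanged, no loss of power is demonstrated, and the cause may be a drafting slip. All of that is fair, and it limits the harm to an undefined recruitment target and the precision that goes with it. It does not remove the need for correction, because the planned sample size is a basic element of the protocol and only the sponsor can say which figure was meant.

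Third, the unsupported beta statement is a separate weakness. That is accepted: it matters here only because it fails to resolve the conflict.

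**Conclusion.** The concern holds. The protocol states two sample sizes for one population, 18 patients apart, and as written at least one is wrong or unlabelled. The conclusion rests on the two sentences alone and needs no assumption about effect size or variability. The 26% difference in standard error assumes the same SD at both sizes. The detectable effects above rest on an assumed paired t-test and show only that beta does not identify n. 80% power can be neither confirmed nor refuted at either size. The documents do not show whether 48 or 30 is the intended number.

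**What to change.** 1. **Needed.** State one target n in both Experimental Design and Methods and Inclusion criteria. If 48 and 30 are different counts, such as enrolled and evaluable, label them so in both places and give the reason for a 37.5% difference. This costs only wording and adds no patients beyond those already stated.
2. **Advisable, but separate.** Tie the alpha and beta sentence in Plans for Data Analysis to the chosen n and to the comparison it was meant for, with effect size, SD, sidedness and source. If no calculation lies behind beta 0.20, delete that statement and give whatever rationale the chosen n does have. This is also wording only, provided a calculation exists or the statement is removed.
3. **Optional.** If an analysis of agreement between each smartphone device and the Masimo is added, state its precision at the chosen n. The 95% CI half-width for a limit of agreement is t(0.975, n−1) × √(1/n + 1.96²/(2(n−1))). That is 0.500 SD of the paired differences at 48 and 0.645 SD at 30, assuming one approximately normal pair per patient for one outcome at one time point. This would add an analysis and is not required to resolve the conflict.
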